## 6.0 Procedures Involved

**Study Design:** We will conduct a multi-site, two-arm, parallel group, patient-randomized, blocked, controlled, pilot trial with 3-month follow up, to determine the impact of sharing audio recordings of clinic visits (AUDIO) on self-management in older adults with diabetes and hypertension, compared to the AVS alone (Usual Care). We will recruit 108 adults (30 patients and approximately 6 clinicians per site),  $\geq 65$  years with diabetes and hypertension over a recruitment period of 3 months. We are primarily interested in determining the feasibility of the trial and acceptability of the AUDIO intervention. We will also explore the impact on the patients' ability to self-manage their care as well as exploratory outcomes, at baseline (T0 = pre-visit) and at regular intervals from enrollment (T1 = 1 week, T2 = 3 month). We will also adhere to the CONSORT Statement extension to randomized pilot and feasibility trials during the trial, publish a study protocol and register the study on ClinicalTrials.gov. Our decision to use a patient level randomized trial design is justified for several reasons: 1) randomization reduces the impact of selection bias and confounding; 2) the risk of contamination is low as audio recordings will be reviewed outside of the clinic and the information will be unique to the each patient; 3) individual-level randomization is more efficient than cluster (e.g. clinic) randomization; 4) the use of blocking further improves the statistical precision of results by ensuring that the key characteristics are balanced across treatment groups, avoiding reliance on statistical models to adjust for any imbalances and 5) we will set up routine evaluations of key operational features of the study design e.g., recruitment rates, intervention use, fidelity - determining the need to make changes/refinements to study procedures throughout the trial.

**6.1 Randomization process:** Patients will be randomly allocated to AUDIO or UC alone using a block-randomization technique with the clinician acting as the blocking variable. Blocks of 2 patients per clinician will be generated to ensure an equal number of patients per clinician will be randomly assigned to the AUDIO and UC arm. The

PROTOCOL TITLE: *The impact of sharing audio recorded clinic visits on self-management in older adults: a multisite trial*

project coordinator at Dartmouth College will prepare and send recruitment materials to each site prior to the beginning of data collection and will prepare the randomization sequence in REDCap. Upon completion of pre-visit baseline assessment (T0), the RA at the study site will reveal the participants group allocation using the randomization feature in REDCap. Patients will be offered an AVS per the usual practice at their clinic, either on paper or via patient portal, but only patients in the AUDIO arm will receive access to audio recordings from the RA to review online at home. The randomization process will be operationalized and supervised by study statistician (Co-I [name]).

**Study procedures:** All participating patients and clinicians will provide informed consent. Clinicians will proceed to complete a brief demographic survey. Patients will proceed to complete the pre-visit baseline assessment surveys. The baseline assessment will be administered in a private area of the waiting room in the clinic, private research office, or an available exam room. Patients will also have the option to complete baseline assessment online in REDCap or over the phone with research staff prior to the clinic visit if they opt for eConsent. We have piloted the administration of the patient surveys with older adults aged 65 or older and estimate that completion will take 20 minutes. After completing the pre-visit baseline assessment, patients will be randomly allocated to AUDIO or UC alone, and informed of which group they have been assigned to. If patients are unable to complete pre-visit surveys prior to meeting with the clinician due to time constraints, the surveys may be completed after the visit. Patients meeting the clinician in person will then be escorted by the RA to the vital sign area to meet a medical assistant and/or back to the waiting room.

Patients randomized to the AUDIO group will have their visit recorded using an electronic tablet; a second study recorder will also be used and act as a backup in case the primary recorder fails. For participants in the AUDIO arm, a sign will be placed on the clinic room door by the RA alerting others that a recording is taking place (see Appendix 6. Recording Sign). Upon completing their visit the RA will demonstrate to patients how to access their recording (see Appendix 7. HealthPal Instructions), and administer the post-visit baseline assessment survey items, specifically the PHQ-8 and GAD-7 surveys, and the Interpersonal Processes of Care Survey (IPC). These tasks may take place in clinic for patients having an in-person visit, or remotely by web conference, telephone, and/or email, for patients having a telehealth visit. Patients will identify times and days that are most convenient for follow up assessments, as well as contact information of a person who could be reached in the event they are unreachable. Patients will receive honorariums to promote retention; a thank you note will be mailed with \$30 (gift card, egift card, or site-specific payment method such as Greenphire) following recruitment and \$20 ( gift card, egift card, or site- specific payment method such as Greenphire) upon completion of each follow-up assessment.

**6.2 Monitoring, tracking, and retention:** RAs will receive standardized training on how

PROTOCOL TITLE: *The impact of sharing audio recorded clinic visits on self-management in older adults: a multisite trial*

to collect data during a two-day 'kick-off' training session prior to patient recruitment. Study data will be directly inputted to electronic surveys using REDCap, providing an opportunity to prevent and monitor missing data. At recruitment, the RA will ask patients for an email and phone number to conduct follow-up assessments (by email and/or telephone calls), and to provide contact details for another person if they cannot be reached for follow-up. Follow-up contact attempts may be made by telephone, email, or post, but will be limited to no more than one attempt per day, for up to two weeks from planned T1 assessment, and three weeks from planned T2 assessment. Patients who cannot be reached by telephone will be approached in the clinic to determine their desire to remain in the study and complete follow-up assessments. or document reason for withdrawal if they do not wish to remain. All attempts to contact patients will be documented in REDCap. We will also conduct weekly workbench reports from the EMR to confirm scheduled visits of recruited patients during the follow-up period.

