Quality of hypertension care	Proportion of patients receiving guideline-concordant care in line with Standards of Medical Care in Hypertension		X	
	T0 (Baseline Assessment; pre-visit); T1 (1 week); T2 (3 months); from enrollment; PAM-SF (Patient Activation Measure Short Form); Global Patient-Reported Outcome Measurement Information System ( PROMIS ); QOL (Quality of life); ER (Emergency Room). ( S ) Spanish language; PROM (Patient Reported Outcome Measure). Note: the Interpersonal Process of care (IPC) survey will be administered after T0 in clinic (or at T1 if not yet completed) AND within 7 days of interim scheduled clinic visits (Tx) during the data collection period.			

PROTOCOL TITLE: *The impact of sharing audio recorded clinic visits on self-management in older adults: a multisite trial*

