use the workbench feature of the Electronic Medical Record in order to generate lists of potential patients of study clinicians, and to check scheduled visits for recruited patients. A waiver of HIPAA Authorization has been applied for with the D-H Privacy Office. An RC in clinic, fluent in English (and in Spanish at our UTMB site where there is a significant portion of patients with Spanish as their preferred language), will review the scheduled appointment list for each upcoming month period from the EMR for patients who meet provisional eligibility criteria. This information will be transferred to a local REDCap Recruitment database for each site, which will only be accessible to IRB approved research staff at those sites. A list of potentially eligible patients will be sent to the study clinician for review, to ensure that they manage the patient's hypertension and diabetes medication. The study clinician will indicate any patients who do not meet the inclusion/exclusion criteria. Potentially eligible patients will receive a letter, signed by their clinician, informing them about the project, that they may be contacted by a member of a research team and offering them the opportunity to opt-out (by email or telephone). No less than two weeks after letters have been sent, an RA will contact patients by telephone to gauge their interest in the project. Patients will be given a number and email address to opt out of receiving a call. For those receiving a telephone call, the RC will briefly describe the project to the patient (Appendix. 9 Telephone Patient Recruitment Script): (1) their clinic visits during the study will be audio- recorded if they are randomly allocated to the AUDIO group for 3 months, or that they will continue to receive UC (an AVS); and (2) there will be a standard follow-up assessment for all study participants via telephone call or email at 1 week, and 3 months; additionally within one- week after any scheduled visit during the 3 month study period, the Interpersonal Processes of Care (IPC) Scale will be administered. Importantly it will be emphasized that willingness to get involved in the project will not affect their care and that no providers in the clinic are opposed to their patient participation. Interested patients will be asked screening questions to establish eligibility. We will gather minimal data on patients who fail screening (demographics, eligibility criteria failed). Patients who are eligible will be asked to arrive at clinic 30 minutes before their scheduled visit and will be reminded that the early arrival will not be indicated in appointment date/time reminders or MyChart/MyDH/MyHealthAtVanderbilt appointment times. Patients will also be sent a reminder letter/email/phone call prior to their scheduled visit (Appendix 10. Appointment Reminder Letter) and will also have the opportunity to complete eConsent and baseline assessment prior to the clinic visit (see Section 22).

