PROTOCOL TITLE: *The impact of sharing audio recorded clinic visits on self-management in older adults: a multisite trial*

patients assigned to UC who self-report that they recorded their visit and listened to the recording to estimate the quantity, the proportion of takers. Our estimator is based the relation with the just described proportions being substituted on the right-hand-side. This procedure corresponds to substituting the estimated value of  $\hat{\pi}$  for  $\pi$  in (1) as the resulting model can be seen as the second-stage of the two-stage least squares procedure adapted to a mixed-effect outcome model.

**17.1.5 Longitudinal use of recordings:** Another extension of our basic analysis will be to analyze the data from the two follow-up time periods (T1–T2) simultaneously using a longitudinal model. An advantage of this analysis is that it allows the form of the trajectory of the outcome variable over the follow-up time (e.g., is it constant, does it have an initial rise at T1 and then decline, does it grow with time) to be compared to a null model having a constant effect. This analysis provides a more powerful test of the effect of AUDIO than a cross-sectional comparison. In both the cross-sectional analyses of the outcome at a single follow-up time and the longitudinal analyses, the inclusion of the baseline (T0) value of the outcome variable as a covariate and/or making the difference in the outcome between  $T_k$  ( $k = 1, 2$ ) and T0 as the outcome are alternative analyses. Because our study is randomized, it is not necessary to include the outcome variable at T0 as a covariate from a bias standpoint, yet, doing so may improve the precision of our results. The chosen strategy will depend on the extent to which the baseline and follow-up outcomes cluster within patients. If clustering is high (e.g., intra-class correlation coefficient  $> 0.5$ ) we will include the T0 value of the outcome variable as a covariate.

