## 22.0 Consent Process

### 22.1 Consent Process (Aim 1 Trial)

#### 22.1.1 Patients (Aim1)

**eConsent:** A link to the consent form will be sent via REDCap immediately after the screening phone call with the RA to eligible interested patients willing to complete eConsent. The eConsent will consist of the same, age-appropriate materials as in-person consent (described below). Patients will be instructed to review the eConsent. Participants will have the ability to move forward or backward on the eConsent form as needed prior to completing consent. A short quiz to confirm patient understanding of the project will be completed electronically as part of the eConsent process - this is a common step in eConsent processes (Appendix 23. eConsent Comprehension Quizzes). Contact information will be available to participants should they have further questions or points needed to be clarified with the study team. Participants will also have the option to provide the name and email of a friend or family member who they involve in their care and would be willing to share their recording with. Those who complete eConsent will leave a digital signature; they will be emailed a copy of their signed eConsent form and will also be offered a mailed paper copy of the consent form. Participant and study staff signatures on the eConsent may have different dates, as participants may sign during non-business hours. Study staff will sign the eConsent electronically as soon as feasible after participant completion. Participants will also receive an email asking them to attend clinic 30 minutes early on the day of the research if they would prefer to complete pre-visit surveys in person rather than electronically. On the day of the visit, a member of the research team will meet with the participant, either in person or by telephone/web conference, and proceed with study procedures.

**In-person consent:** For participant who prefer to complete consent in clinic, they will be met by the RA in the clinic waiting room. A member of the registration staff may also receive a list of patients who have agreed to learn more about the project, to facilitate a warm hand-off of patients to the RA. Patients will join the RA in a private room/area where they will confirm inclusion and exclusion criteria with the patient. This will be done using a short, standardized screening form. Once it is determined that the

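### T1 and T2 are counted from an undefined enrollment date, so the schedule permits a 1-week assessment before the visit that produces the recording

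*Combined protocol and SAP*

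**What the plan says.** **The anchor.** Section 6.0 (Study Design) schedules the follow-up assessments "at regular intervals from enrollment (T1 = 1 week, T2 = 3 month". The Table 1 footnote in section 4.2 repeats this: "T0 (Baseline Assessment; pre-visit); T1 (1 week); T2 (3 months); from enrollment". The enrollment date is not defined. Section 18.1 monitors enrollment through consent.

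**What may precede the visit.** Section 13.1 has the coordinator "review the scheduled appointment list for each upcoming month period", with at least two weeks between the invitation letter and the screening call. Section 22.1.1 then says "A link to the consent form will be sent via REDCap immediately after the screening phone call with the RA". Patients who choose eConsent have the "option to complete baseline assessment online in REDCap or over the phone with research staff prior to the clinic visit" (section 6.0, Study procedures), and allocation follows the pre-visit baseline. No section caps the interval from consent or allocation to the visit, and none requires T1 to follow the visit.

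**The window.** Section 6.3 (Assessments) lets T1 run up to two weeks, and T2 up to three weeks, from the scheduled point. Assessments outside the window are reported to the IRB.

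**Text that presumes a post-visit T1.** The Table 1 footnote says the Interpersonal Processes of Care survey (IPC), which rates the visit, "will be administered after T0 in clinic (or at T1 if not yet completed". Section 6.4.1 asks about use of the after-visit summary at the standard assessments. The PHQ-8 and GAD-7 are T0 measures in Table 1, yet sections 6.0 and 6.3 give them after the visit.

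**The analyses that use T1.** Section 17.1.5 models T1 and T2 jointly and asks of the trajectory: "does it have an initial rise at T1 and then decline, does it grow with time". Section 17.1.6 relies on the 1-week and 3-month data to regress health outcomes on lagged PAM-SF.

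**The concern.** The intervention begins at the index visit: before it there is no recording to hear. The listening regime in section 5.1.1 also runs from the visit, with the first listening within a day and another at one week. The assessment clock runs from a different event, which may come earlier for patients who eConsent.

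For a patient whose visit falls after the T1 assessment, T1 is in effect a second baseline. Pooled with genuine post-visit assessments, it pulls the AUDIO-UC difference at T1 toward zero while leaving T2 largely intact. An effect that is constant once the recording is available can then look as if it grows over follow-up, which is one of the shapes section 17.1.5 sets out to distinguish. A pre-visit PAM-SF also cannot carry an effect of the recording into the lagged mediation analysis. At T2, time since the first recording would vary with how early the patient enrolled.

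The pilot is not powered for outcomes, but section 17.1.10 wants its effect estimates to inform the size of the next trial.

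**Working it through.** The plan states no enrollment-to-visit interval, no eConsent share, and no effect size or SD for the outcomes, so it has no figure of its own to reproduce. All lag, uptake, effect and correlation values below are assumptions that show scale.

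**1. Timing condition.** Let L be the days from enrollment to the index visit. From section 6.3, T1 is scheduled on day 7, and the window ends on day 7 + 14 = 21, if only late completion is allowed.
- L ≤ 7: T1 cannot precede the visit.
- L between 7 and 21: it can, depending on when in the window T1 is done.
- L > 21: an in-window T1 always precedes it.

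**2. How long L could be.** Take the month-ahead list as 30 days, with letters sent the same day and the call on day 14. Then L is at most 30 − 14 = 16 days. Without that same-day link between list and letter, allow up to 30 days. With L uniform, the share of early-eConsent patients whose T1 precedes the visit is:

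| Maximum L | T1 on day 7 | T1 spread over days 7–21 | T1 on day 21 |
|---|---|---|---|
| 7 days | 0% | 0% | 0% |
| 16 days | 9/16 = 56% | 18% | 0% |
| 30 days | 23/30 = 77% | 53% | 9/30 = 30% |

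**3. Share of all patients.** Multiply by the fraction who eConsent early. Using the 56% cell, uptake of 25%, 50% or 100% gives f = 0.14, 0.28 or 0.56. With T1 on day 21 and L up to 16 days, f = 0.

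**4. Effect on the T1 contrast.** With a constant true effect d, the T1 effect is d(1 − f) and the apparent growth from T1 to T2 is f × d. Sample size is 90 patients, 45 per arm. The standard error of the arm difference in change is √(2(1 − ρ)) × √(2/45), or 0.21 SD at ρ = 0.5 and 0.16 SD at ρ = 0.7. Tests are two-sided at 0.05.

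| d | f | T1 effect | Apparent growth | Power at T1 | Chance of rejecting a constant effect (ρ 0.5–0.7) |
|---|---|---|---|---|---|
| 0.3 | 0 | 0.30 | 0 | 30% | 5% |
| 0.3 | 0.14 | 0.26 | 0.04 | 23% | 6% |
| 0.3 | 0.28 | 0.22 | 0.08 | 18% | 7–8% |
| 0.3 | 0.56 | 0.13 | 0.17 | 9% | 13–18% |
| 0.5 | 0 | 0.50 | 0 | 66% | 5% |
| 0.5 | 0.14 | 0.43 | 0.07 | 53% | 6–7% |
| 0.5 | 0.28 | 0.36 | 0.14 | 40% | 10–14% |
| 0.5 | 0.56 | 0.22 | 0.28 | 18% | 26–40% |

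**5. Exposure at T2.** Taking 3 months as 91 days, post-visit time at T2 is 91 − L: 84 days (92%) at L = 7, 75 days (82%) at L = 16, and 61 days (67%) at L = 30.

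**6. With T1 anchored to the visit.** Then f = 0: the T1 effect stays at d and the test of a constant effect keeps its 5% level. The sample size does not change.

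**The case against.** The strongest reply is that the authors plainly meant T1 to follow the visit, so this is only an undefined term. Baseline itself is not finished until the PHQ-8 and GAD-7 have been given after the visit, IPC may be collected at T1, and AVS use is asked there. This stands as evidence of intent. It does not settle the rule: staff who apply section 6.0 and the Table 1 footnote as written would count one week from enrollment, and the texts would then conflict.

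A second reply is that the case is rarer than it looks. The two-week wait after the letter limits the lag to about 16 days on a 30-day list, and the T1 window to day 21 leaves room for a post-visit assessment. This also stands, and step 2 shows that the share can be zero.

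Four stronger readings are tempting, and the documents do not support them:
- *Patients are randomized online before the visit.* Baseline may be completed online, and allocation follows baseline, but the site research assistant reveals it. For eConsent patients, section 22.1.1 has the team meet the participant on the visit day and continue from there. Early allocation is permitted, not prescribed.
- *The trajectory analysis is distorted.* It can be. Whether it is depends on lags and uptake that the documents do not report.
- *The effect is diluted in both arms.* The effect is a contrast between arms, and usual care has no AUDIO effect to dilute.
- *Consent mode biases the comparison.* Consent precedes allocation and both arms follow the same schedule, so the randomization holds.

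Finally, counting from the visit has a weakness of its own. Where allocation comes first, the visit is a post-randomization event, and a patient who misses it would have no T1 or T2 date. This stands, and the fix has to provide for it.

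**Conclusion.** The point holds as an unresolved and internally inconsistent time origin. T1 and T2 run from an undefined enrollment date, pre-visit eConsent and baseline are allowed with no cap on the lag, and nothing places T1 after the visit. The schedule therefore permits a T1 that cannot reflect the intervention, against other text that presumes the opposite.

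The size cannot be determined from the documents. Under the assumptions in steps 2 to 4, f runs from 0 to 0.56 for lags up to 16 days. At the middle value of 0.28, the false growth of 0.08 to 0.14 SD is below its own standard error of 0.16 to 0.21 SD; it becomes material only if early eConsent is common and T1 is done promptly on day 7. The 16-day loss of exposure at T2 is shorter than the three-week T2 window already allowed.

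The consequences are confined to exploratory work: the T1 contrast, the trajectory model in section 17.1.5, the lagged mediation in section 17.1.6 and, through shorter exposure only, PAM-SF at 3 months. A reader might infer that the primary endpoints are compromised; feasibility and acceptability do not depend on this anchor. The correction is worth making because it is cheap and removes a real conflict in the text.

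**What to change.** 1. Define the enrollment date.
2. Count T1 and T2 from the index clinic visit in both arms, keeping the present windows.
3. If the index visit is cancelled or missed, use its originally scheduled date as day 0, so that every randomized patient keeps follow-up dates.
4. Reconcile the Table 1 footnote (4.2), the Study Design paragraph (6.0), Assessments (6.3) and the AVS-use text (6.4.1), and set the REDCap survey schedule to match.
5. Record the visit-to-T1 interval. If follow-up has already begun, add a sensitivity analysis of the T1 contrast and the T1–T2 trajectory by time since the index visit, in both arms.

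The cost is wording and a date field in REDCap, where scheduled visits are already documented (sections 5.1.2 and 18.2). The downside is that T1 and T2 move when the index visit is postponed, and that missed visits need the fallback date. Section 25.0 reports 7% cancellations at the Dartmouth-Hitchcock site; if that rate applied to index visits, it would concern about 0.07 × 30 ≈ 2 patients there.

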## 4.0 Study Endpoints\*

### 4.1 Primary endpoint

The primary endpoints of this pilot trial are:

1) Feasibility: We will determine the optimal strategy to achieve a high retention rate and adherence to the study protocol. We will also assess retention rates (proportion of included patients completing T2 follow up; we will target >70%), fidelity to the study protocol (Borrelli et al criteria; we will target >90%) and the Feasibility of Intervention Measure (FIM, 4 items, see Appendix 1. 3-month Follow Up Assessment (T2); we will target an average score of >3).

2) Acceptability: We will determine the acceptability of the AUDIO intervention and study protocol by assessing the proportion of patients and clinicians who agree to take part in the project and proportion of patients who listen to the recording. Our primary indicator of acceptability will be the recruitment of 108 participants (N=30 patients and 6 clinicians per site) over our planned data collection period of six months. We will determine the listening rates (we will target >70%): this will include the proportion of patients in the intervention arm that log in to the online system and listen to (and how often) the recording. We will also document the number of patients who share or report sharing the recording and caregivers who access the recording. Participants will complete the Acceptability of Intervention Measure (AIM, 4 items, see Appendix 1. 3-month Follow Up Assessment (T2); target an average score of >3).

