**Assessments:** A trained RA will collect data (**T0**= Baseline Assessment) by electronic tablet or by paper form if preferred by the patient prior to the visit. Patients who complete eConsent can also complete the baseline assessments via REDCap prior to the clinic visit. The PHQ-8 and GAD-7 will be administered after the clinic visit. Follow up is planned by email (Appendix 25 for the REDCap Survey Template) or telephone at **T1**= one week, **T2**= three months. For T1, the allowable window is up to two weeks from the scheduled timepoint. For T2, the allowable window is up to three weeks from the scheduled timepoint. Deviations from the follow up strategy (e.g., a patient who completes an assessment outside of the planned follow up window) will be reported to the IRB. No participant identifiers will be included on the labeling of study data. Study Unique ID code numbers instead of names will be used on participant materials, data and data-collection instruments to minimize risks regarding breach of confidentiality.

Patients will receive a printed schedule of follow-up assessments, tailored to times and days convenient to them.

Outside of the standard study follow up assessments, the patient will be met in clinic or contacted by email or telephone one week from any scheduled visit with a participating clinician to assess intervention use (AVS or AUDIO) and interpersonal processes of care (IPC) survey (immediately following the clinic visit, or within 1 week of the visit by email or telephone with the RA).

**6.4 Outcomes:** Our primary and exploratory outcome measures are outlined in Section 4.2 Table 1.

**6.4.1 Covariates:** Demographic information (age, sex, race, ethnicity, language used at home, educational attainment using categories from the 2016 American Community Survey) will be collected by the RA through patient report at enrollment. We will document if a caregiver (a support person, family member or friend) is present at the visit. We will collect demographic and practice information about participating clinicians including their age, sex, race, ethnicity and years in practice. The following covariates will be examined in our exploratory moderator analysis:

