## 25.0 Resources Available

We are confident we can recruit the necessary number of patients at each site. D-H offers primary and specialty-care services, with 35 primary care clinicians, where in 2017, there were 1,144 unique patients  $\geq 65$  years with multimorbidity and at least 2 visits in the preceding 7 months, with only 7% cancellations. Like the geographic region it serves, the D-H clinic population is predominantly white, non-Hispanic (94%). The VUMC Adult Primary Care consists of two sites located on the VUMC campus; and two sites in the community. These four clinics are staffed by > 59 attending physicians. In 2017, they saw 1,500 unique patients  $\geq 65$  with multimorbidity. UTMB clinics are staffed by 11 attending clinicians, with 1,805 unique patients aged  $\geq 65$  with multimorbidity in 2017. We will have dedicated research assistants, with CITI training, who will lead in clinic recruitment. Each site has the necessary resources, infrastructure and experience of conducting trials. All research staff will meet for a 2-day training hosted by Dartmouth College, prior to recruitment and study PIs will meet together prior to the commencement of recruitment and at the end of data collection. Finally all clinic staff will be informed and educated about the project over the course of several presentations at standing clinical team meetings and one-on-one meetings with participating clinicians.

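### Allocation is released when baseline is complete, so patients with a remote baseline can be randomised and told their arm before an index visit that is then cancelled

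*Combined protocol and SAP*

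**What the plan says.** Section 6.1 ties disclosure to the baseline assessment: "Upon completion of pre-visit baseline assessment (T0), the RA at the study site will reveal the participants group allocation". The Study procedures text in 6.0 repeats the order: "After completing the pre-visit baseline assessment, patients will be randomly allocated to AUDIO or UC alone, and informed of which group". Neither sentence makes allocation depend on attendance.

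The same text allows the baseline to be done remotely by patients who choose eConsent: "Patients will also have the option to complete baseline assessment online in REDCap or over the phone with research staff prior to the clinic visit". Section 6.3 (Assessments) confirms it: "Patients who complete eConsent can also complete the baseline assessments via REDCap prior to the clinic visit". Section 13.1 offers the same option. Section 22.1.1 shows how early the sequence can start: "A link to the consent form will be sent via REDCap immediately after the screening phone call". It also says of eConsent patients: "On the day of the visit, a member of the research team will meet with the participant", after which study procedures go ahead. It does not say whether randomisation is one of those procedures.

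Section 4.1 defines the listening rate, with a target above 70%, as "the proportion of patients in the intervention arm that log in to the online system and listen to" the recording; 17.1.2 repeats this. Retention, also with a target above 70%, is a proportion of included patients, a term that is not defined.

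Sections 5.1.2 and 18.2 have the research assistant (RA) attend and record each scheduled visit of AUDIO patients. Section 5.1.2 expects one additional scheduled visit in the three months.

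**The concern.** Because completing the baseline is the trigger, the gap between allocation and the index visit depends on how the baseline was done. In clinic it is minutes. For a remote baseline it can be as long as the interval from the screening call to the appointment. If the visit is cancelled in that gap, the patient is already randomised and knows the arm.

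The documents give no rule for this case. Section 14.0 (Withdrawal) does not cover it and no analysis population is defined. Section 17.1.4 foresees AUDIO patients who get no recording, but only for an instrumental-variable analysis of the exploratory outcomes.

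Feasibility and acceptability are the primary endpoints here. A patient who had nothing to listen to says something about scheduling, not about the acceptability of recordings. If that patient counts as a non-listener, the listening rate mixes the two, and the mix varies with each site's share of remote baselines. Sites reading 6.1 and 22.1.1 differently would also randomise at different moments.

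**Working it through.** **Inputs from the documents**
- Patients: 3 sites × 30 = 90. With 6 clinicians per site, 3 × (30 + 6) = 108, which reproduces the stated total (26.0).
- Allocation 1:1 in blocks of 2 within clinician (6.1), so about 45 AUDIO patients, assuming overall balance.
- Listening target above 70% (4.1, 17.1.2).
- Cancellations: "with only 7% cancellations" (25.0), for D-H in 2017. No figure is given for the other two sites.

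**Assumptions, not in the documents**
- Share of baselines done remotely before the visit: 25%, 50% or 100%.
- The 7% applies to index visits at all sites.
- True listening rate among patients with a recording: 75%, or 82% as a second case. The 82% is borrowed from 3.2.2, where 28 of 34 interviewed patients and caregivers reported listening. That is a different, self-reported setting.

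**Step 1. Patients allocated before a visit that is then cancelled.** Expected number = patients × 0.07 × remote share.

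| Remote share | AUDIO (of 45) | Both arms (of 90) |
|---|---|---|
| 25% | 0.8 | 1.6 |
| 50% | 1.6 | 3.2 |
| 100% | 3.2 | 6.3 |

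These are upper limits for AUDIO patients without any recording, because a rescheduled or later scheduled visit would be recorded. Missed appointments may not be included in the 7%.

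**Step 2. Listeners needed.** 31/45 = 68.9% misses the target and 32/45 = 71.1% meets it, so 32 listeners are needed.

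**Step 3. Effect of never-recorded AUDIO patients who stay in the denominator.** With k such patients, all 32 listeners must come from 45 − k. The rate needed is 32/(45 − k), and the chance of meeting the target is P(X ≥ 32) with X binomial(45 − k, p).

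| k | Rate needed among recorded | Chance, p = 75% | Chance, p = 82% |
|---|---|---|---|
| 0 | 32/45 = 71.1% | 0.78 | 0.98 |
| 1 | 32/44 = 72.7% | 0.71 | 0.96 |
| 2 | 32/43 = 74.4% | 0.61 | 0.93 |
| 3 | 32/42 = 76.2% | 0.51 | 0.88 |

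**Step 4. Denominator limited to patients with a recording.** For k = 3, exceeding 70% of 42 needs 30 listeners (71.4%). The chance is then 0.77 at p = 75%, against 0.51 when the three are counted. Most of the change in Step 3 therefore comes from the denominator.

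**Retention.** Exceeding 70% of 90 needs 64, since 63/90 is exactly 70%. If 6 never-seen patients counted as included and were all lost, the rest would need 64/84 = 76.2%. Whether they count cannot be settled from the text.

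**The case against.** The strongest reply is that the protocol may already intend allocation on the visit day. Section 22.1.1 has the team meet eConsent patients that day. The Study procedures text moves from allocation to escorting in-person patients to the vital-sign area. Revealing the arm is also an action by the RA in REDCap, not an automatic release when a survey is submitted. This stands as far as it goes: the timing for remote baselines is ambiguous. It does not remove the gap, because both sentences that set the trigger name completion of the baseline and the visit-day sentence does not name randomisation.

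Three stronger readings are tempting and not supported.
- A reader might infer that a cancelled index visit means no recording at all. Sections 5.1.2 and 18.2 record later scheduled visits, so this is true only if no scheduled visit takes place during follow-up.
- A reader might take the fall from 0.78 to 0.51 as the expected effect. It needs roughly 100% remote baselines, no rescheduling and a listening rate close to the target. The 7% is also a general clinic figure, while study patients receive reminders (13.1).
- A reader might infer that patients will cancel because of their arm. Knowing the arm in an open trial makes this possible, but nothing in the documents shows it.

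It is also fair that HealthPAL logs, the fidelity checklist and recorded reasons for loss would let the team separate the causes afterwards. Keeping all randomised patients is right for the between-arm comparison. Neither point settles the denominator of the listening rate.

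**Conclusion.** The point holds as a gap in the allocation rule with a modest effect. A site that follows 6.1 as written can randomise and inform a patient whose index visit then does not happen, and the plan does not say how that patient is handled. For the listening rate, counting such a patient as a non-listener follows from the literal definition. For retention it remains open.

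The likely size is at most about 1 to 3 AUDIO patients of 45. That matters only if listening is near 70%: at an assumed 75% even one or two such patients lower the chance of meeting the target to 0.71 or 0.61, while at 82% it stays at 0.88 or above with three. These figures rest on 45 patients per arm, one site's 2017 cancellation rate applied everywhere, and assumed remote shares and listening rates. The change is worth making because it is cheap and prevents avoidable loss after randomisation.

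**What to change.** In 6.1, keep eConsent and the remote baseline, and add that the RA releases the REDCap allocation only on the day of the index visit, once attendance is confirmed: check-in for in-person visits, confirmed contact with the patient for telehealth. Release must be early enough for the recording instructions and demonstration in 5.2. Patients whose visit does not take place stay un-randomised and are rescheduled or replaced.

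In 4.1 and 17.1.2, report the listening rate both for all AUDIO patients and for those with at least one recording. Define included patients for the retention rate.

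While editing, reconcile one nearby sentence. The Study procedures text lets the pre-visit surveys be completed after the visit when time is short, yet allocation follows those surveys and an AUDIO visit cannot be recorded before allocation.

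The cost is a few sentences in the protocol and RA instructions, and shorter notice of which visits to record. This is tightest for telehealth, where the RA either trains the clinician in the room or joins by link. In-clinic baselines already work on similar notice.
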